9.6 Unscheduled Visits

Additional visits (not specified in [Table 16](#)) may be conducted for PB assessment, BM aspirate/biopsy, chemistry assessment, or AE evaluation, at the investigator's discretion.

9.7 Missed Evaluations

Evaluations should occur within the visit window specified by the protocol. If an evaluation is missed, reschedule and perform it as close as possible to the original date. If rescheduling becomes, in the investigator's opinion, medically unnecessary because the evaluation would occur too close to the next scheduled evaluation, it may be omitted.

10.0 EVALUATION, RECORDING, AND REPORTING OF ADVERSE EVENTS

10.1 Definitions

10.1.1 Adverse Event (AE)

Adverse Event (AE): Any untoward medical occurrence associated with the use of a drug in humans, whether or not considered drug related. An AE can therefore be any unfavorable and unintended sign (including a clinically significant abnormal finding in laboratory tests or other diagnostic procedures), symptom, or disease temporally associated with the use of a drug, without any judgment about causality. An AE can arise from any use of the drug and from any route of administration, formulation, or dose, including an overdose.

Disease progression is not considered to be an AE or SAE. If there are specific AEs that are always part of disease progression, these do not need to be reported as AEs or SAEs. Pre-existing medical conditions (other than natural progression of the disease being studied) judged by the investigator or subject to have worsened in severity or frequency or changed in character during the protocol-specified AE reporting period will be reported as AEs or SAEs as appropriate.

An AE or SAE can also be a complication that occurs as a result of protocol mandated procedures (eg, invasive procedures such as biopsies).

10.1.2 Serious Adverse Events (SAEs)

An AE is considered serious, if in the view of either the investigator or sponsor, it results in any of the following outcomes:

- Death.
- A life-threatening AE.

An AE is considered "life-threatening" if in the view of either the investigator, or sponsor, its occurrence places the subject at immediate risk of death. It does not include an AE that, had it occurred in a more severe form, might have caused death.

- Inpatient hospitalization or prolongation of an existing hospitalization.
- A persistent or significant incapacity or substantial disruption of the ability to conduct normal life functions.
- A congenital anomaly or birth defect.

Important medical events that may not result in death, be life-threatening or require hospitalization may be considered serious when, based on the appropriate medical judgment, they may jeopardize the subject and may require medical or surgical intervention to prevent one of the outcomes listed in the definition of SAE. Examples of such medical events are intensive treatment in an emergency room or at home, blood dyscrasias or convulsions that do not result in inpatient hospitalization, or development of drug dependency or drug abuse. For clarification, Grade 3 or 4 cytopenias that are not associated with a life-threatening or otherwise medically

significant clinical AE as defined above, and do not result in hospitalization, are not considered SAEs.

10.2 Adverse Event Reporting and Descriptions

Record new AEs from the start of study treatment until 30 days after the last dose of study treatment (ie, discontinuation of treatment in the study) or until the subject starts new anti-leukemic treatment, including new investigational treatment. Also record screening procedure-related AEs that occur before the start of study treatment.

Record all treatment-emergent AEs (AEs occurring after the start of study treatment) either observed by the investigator or one of his or her medical collaborators, or reported by the subject spontaneously, or in response to the direct question below, in the AEs section of the subject's CRF/eCRF, in the source document, and if applicable, record on the SAE form. Whenever possible, the investigator should group signs and symptoms (including laboratory tests or other results of diagnostic procedures) into a single diagnosis under a single term. For example, cough, rhinitis, and sneezing might be reported as "upper respiratory infection" or a pulmonary infiltrate, positive sputum culture and fever might be reported as "pneumonia."

To optimize consistency of AE reporting across centers, ask the subject a standard, general, non-leading question to elicit any AEs (such as "Have you had any new symptoms, injuries, illnesses since your last visit?").

Death is an outcome of an SAE and usually not itself an SAE, unless it is death with no identifiable cause or event. In all other cases, record the cause of death as the SAE. Investigators will assess the status of previously reported, and occurrence of new, AEs and SAEs at all subject evaluation time points during the study.

10.2.1 Severity

Use the definitions found in the Common Terminology Criteria for Adverse Events (CTCAE) v4.03 for grading the severity (intensity) of AEs ([Appendix 3](#)). The CTCAE v4.03 displays Grades 1 through 5 with unique clinical descriptions of severity for each referenced AE. Should a subject experience any AE not listed in the CTCAE v4.03, use the following grading system to assess severity:

- Grade 1 – Mild; asymptomatic or mild symptoms; clinical or diagnostic observations only; intervention not indicated.
- Grade 2 – Moderate; minimal, local or noninvasive intervention indicated; limiting age-appropriate instrumental activities of daily living (ADL), such as preparing meals, shopping for groceries or clothes, using the telephone, managing money, etc.

- Grade 3 – Severe or medically significant but not immediately life-threatening; hospitalization or prolongation of hospitalization indicated; disabling; limiting self-care ADL, such as bathing, dressing and undressing, feeding self, using the toilet, taking medications, and not bedridden.
- Grade 4 – Life-threatening consequences; urgent intervention indicated.
- Grade 5 – Death related to AE.

10.2.2 Relationship to Study Treatment (Suspected Adverse Reactions)

Assess all AEs/SAEs for relationship to study treatment or if applicable, to study procedure.

If an AE/SAE occurs before the first dose of study treatment, report it only if it is considered related to a study-specific procedure (eg, bleeding or local infection after skin punch biopsy). Those events will be recorded in the study database but will not be part of the treatment-emergent AE analysis.

To ensure consistency of AE and SAE causality assessments, investigators should apply the general guideline shown below. Multi-drug regimens should have a causality assessment of each component to aid in analysis.

Related (Suspected Adverse Reaction)	
A suspected adverse reaction means any AE for which there is a reasonable possibility that the drug caused the AE. Reasonable possibility means there is evidence to suggest a causal relationship between the drug and the AE such as a plausible temporal relationship between the onset of the AE and administration of the drug; and/or the AE follows a known pattern of response to the drug; and/or the AE abates or resolves upon discontinuation of the drug or dose reduction and, if applicable, reappears upon rechallenge. Further examples of type of evidence that would suggest a causal relationship between the drug and the AE:
 
• A single occurrence of an event that is uncommon and known to be strongly associated with drug exposure (eg, angioedema, hepatic injury, Stevens-Johnson Syndrome),• One or more occurrences of an event that is not commonly associated with drug exposure, but is otherwise uncommon in the population exposed to the drug (eg, acute myocardial infarction in a young woman),• An aggregate analysis of specific events observed in a clinical study (such as known consequences of the underlying disease or condition under investigation or other events that commonly occur in the study population independent of drug therapy) that indicates those events occur more frequently in the drug treatment group than in a concurrent or historical control group.
--	---

Not Related Adverse events that do not meet the definition above.
(Not Suspected)

10.2.3 **Pregnancy and Abortion**

Report any pregnancy that occurs in a subject or male subject's female partner during the time between the first study-specific procedure and 60 days after the last dose of study treatment. Record any occurrence of pregnancy on the Pregnancy Report Form Part I and send to Astex Pharmaceuticals Drug Safety within 24 hours of learning of the event. After the birth of the baby, collect additional information on the baby until the baby is 1 year old by completing the Pregnancy Report Form Part II.

A subject must immediately inform the investigator if the subject or subject's partner becomes pregnant during the time between the first study-specific procedure and 60 days after the last dose of study treatment. Any female subjects receiving study treatment who become pregnant must immediately discontinue study treatment. The investigator should counsel the subject, discussing any risks of continuing the pregnancy and any possible effects on the fetus.

Report any abortion and the reason for it, whether therapeutic, elective, or spontaneous, to Astex Pharmaceuticals Drug Safety within 24 hours, through the SAE reporting process (Section 10.3).

10.3 **Reporting and Evaluation of Serious Adverse Events**

10.3.1 **Reporting Requirements for Serious Adverse Events (SAEs)**

All SAEs regardless of causality will be reported by the investigator to Astex Pharmaceuticals through the 30-day period after the last dose of study treatment. Deaths and SAEs occurring after the 30-day safety follow-up period AND considered related to study treatment or study procedures must also be reported.

Report all SAEs (initial and follow-up information) on an SAE form and send the form to Astex Pharmaceuticals Drug Safety, or designee, within 24 hours of the discovery of the event or information (see below). Astex Pharmaceuticals may request follow-up and other additional information from the investigator (eg, hospital admission or discharge notes, laboratory results).

Astex Pharmaceuticals Drug Safety Contact Information	
PRIMARY CONTACT: Email	██
Global Phone	██
North America Toll-Free Fax	██

Report all deaths with the primary cause of death as the SAE term, as death is the outcome of the event, not the event itself. If an autopsy was performed, report the primary cause of death on the autopsy report as the SAE term. Forward autopsy and postmortem reports to Astex Pharmaceuticals Drug Safety, or designee, as outlined above.

If study treatment is discontinued, temporarily suspended, or dose reduced because of an SAE, include this information in the SAE report.

Suspected Unexpected Serious Adverse Reactions (SUSARs) are SAEs that qualify for mandatory expedited reporting to regulatory authorities where the SAE is suspected to be caused by the study treatment and is considered unexpected (ie, not defined as expected in the current IB, clinical study protocol, or approved labeling for marketed drugs). In this case, Astex Pharmaceuticals Drug Safety or designee will report to the relevant regulatory authorities and forward a formal notification describing the SUSAR to investigators, according to regulatory requirements. Each investigator must then notify his or her IRB/IEC of the SUSAR as required by local regulatory authorities and in accordance with IRB/IEC policy.

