7. Women of child-bearing potential must not be pregnant or breastfeeding and must have a negative pregnancy test at screening. Women of child-bearing potential and men with female partners of child-bearing potential must agree to practice 2 highly effective contraceptive measures during the study and for at least 3 months after completing treatment and must agree not to become pregnant or father a child while receiving treatment with SGI-110 and for at least 3 months after completing treatment. Contraceptive measures which may be considered highly effective comprise combined hormonal contraception (oral, vaginal, or transdermal) or progestogen-only hormonal contraception (oral, injectable, implantable) associated with inhibition of ovulation, intrauterine device, intrauterine hormone-releasing system, bilateral tubal occlusion, sexual abstinence, and surgically successful vasectomy. Abstinence is acceptable only if it is consistent with the preferred and usual lifestyle of the subject. Periodic abstinence (eg, calendar, ovulation, symptothermal, or postovulation methods) and withdrawal are not acceptable methods of birth control.

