8.0 RISKS/PRECAUTIONS

Refer to the SGI-110 IB for the most current risks and precautions, as well as a complete list of AEs considered expected with SGI-110 therapy.

Common AEs observed in the AML/MDS population treated with SGI-110 include injection site AEs, febrile neutropenia, thrombocytopenia, anemia, diarrhea, fatigue, and nausea. The most common SAEs were febrile neutropenia and pneumonia. MDS and AML subjects commonly have severely compromised BM and blood counts. Severe or prolonged myelosuppression have been reported as related to SGI-110, particularly on high doses (ie, ≥ 125 mg/m²). Two AML/MDS subjects (1 MDS and 1 AML of 357 subjects total) treated with SGI-110 had drug-related SAEs of sepsis with an outcome of death at doses of 125 mg/m²/day for 5 days (MDS) and 18 mg/m²/day for 5 days (AML).

Refer to Section 7.3 for guidelines to adjust study treatment dose.

Injection site reactions, such as pain, irritation, inflammation, erythema, and burning have been reported in the AML/MDS population and in subjects with solid tumors. Injection site reactions are related to SGI-110 SC administration. Care must be taken to avoid intradermal injection. Administer SGI-110 by slow SC injection. If injection site pain is reported upon injection, apply ice packs to the injection site both before and after injection. If injection site AEs are reported at subsequent injections despite slow injection and use of ice packs, pretreatment with topical or systemic analgesics can be considered.

Use of decitabine, the active metabolite of SGI-110, alters fertility and is mutagenic. Because of the possibility of infertility, men should seek advice on conservation of sperm, and women of child-bearing potential should seek consultation regarding oocyte cryopreservation before study treatment is started.

For risks and benefits of TC therapies, refer to the latest locally-approved Prescribing Information for each therapy (USA examples: [Cytarabine 2008](#), [Dacogen 2010](#), [Vidaza 2014](#)).

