9.5.5 Treatment Discontinuation and Safety Follow-up Visit

Each subject should be followed up, to document the occurrence of any new AEs, for at least 30 (+7) days after his or her last dose of study treatment, or until any AE or SAE assessed as related to study treatment or procedures has resolved to a clinically acceptable or stable resolution (see Section 10.4). Subjects who withdraw consent should still be encouraged to complete this visit. The following evaluations are to be performed:

- Complete physical examination.
- Vital signs.
- ECOG performance status.
- 12-lead ECG (triplicate).
- Health-related QOL EQ-5D-5L (Appendix 4).
- All AEs and concomitant medications.
- Sample collection for clinical laboratory tests, including:
 - Hematology (see Table 17).
 - Serum chemistry (see Table 17).
- Serum or urine pregnancy test: for women of child-bearing potential only.
- Hospital admission and discharge dates (and the main reason for hospitalization), as well as all blood and platelet transfusions (blood product transfused and units), since the last visit.
- Subsequent anti-leukemia therapy (regimen and start date).
- Disease progression status (subjects who discontinue treatment before documented disease progression must undergo PB and BM aspirate/biopsy assessments until disease progression or relapse is confirmed).

The treatment discontinuation and safety follow-up visit may be conducted by telephone if needed to collect, at minimum, AE information.

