9.5.6 Long-term Follow-Up

Long-term follow-up starts after subjects discontinue study treatment. Long-term follow-up visits will be either monthly or every 3 months, depending on when the subject discontinues study treatment:

- For subjects who discontinue treatment before Cycle 6, initial follow-up visits will be conducted monthly (± 7 days) until 6 months after the start of study treatment, and then visits will be conducted every 3 months (± 2 weeks), until death.
- For subjects who discontinue treatment after Cycle 6, long-term follow-up visits are required every 3 months (± 2 weeks), until death.

Monthly long-term follow-up procedures (for subjects who discontinue treatment before Cycle 6):

- Health-related QOL EQ-5D-5L ([Appendix 4](#)).
- Hospital admission and discharge dates (and the main reason for hospitalization), as well as all blood and platelet transfusions (blood product transfused and units), since the last visit.
- Subsequent anti-leukemia therapy (regimen and start date).
- For subjects with no documented disease progression on treatment:
 - Hematology and/or BM aspirate/biopsy (≥ 1 year after the start of study treatment, BM aspirate/biopsy every 6 months) until disease progression or relapse is documented.
 - Disease progression status.
- Survival follow-up.

Long-term follow-up procedures for visits every 3 months (± 2 weeks) (for subjects who discontinue treatment after Cycle 6 and for subjects have completed the monthly long-term follow-up visits described above):

- Subsequent anti-leukemia therapy (regimen and start date).
- For subjects with no documented disease progression:
 - Hematology and/or BM aspirate/biopsy (≥ 1 year after the start of study treatment, BM aspirate/biopsy every 6 months).
 - Disease progression status.
- Survival follow-up.

Long-term follow-up visits may be conducted by telephone if needed.

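### Pregnancy reporting stops 60 days after the last dose, about 30 days before the protocol's own 3-month conception-avoidance period ends

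*Protocol*

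**What the plan says.** Protocol Section 10.2.3 (Pregnancy and Abortion) uses the same time limit twice. The investigator must report a pregnancy in a subject, or in a male subject's female partner, that occurs "during the time between the first study-specific procedure and 60 days after the last dose of study treatment". The subject's own duty to tell the investigator carries the identical limit. A report starts Part I of the pregnancy form. After the birth, the site must "collect additional information on the baby until the baby is 1 year old by completing the Pregnancy Report Form Part II".

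Inclusion criterion 7 (Section 5.2, repeated in the Synopsis) sets a longer period. Women of child-bearing potential, and men with such partners, must use two highly effective contraceptive measures for at least 3 months after treatment. They "must agree not to become pregnant or father a child while receiving treatment with SGI-110 and for at least 3 months after completing treatment". Section 8.0 supplies a reason for caution: "Use of decitabine, the active metabolite of SGI-110, alters fertility and is mutagenic".

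Two other reporting duties run past day 60. Section 10.2.3 states, without a time limit, "Report any abortion and the reason for it, whether therapeutic, elective, or spontaneous". Section 10.3.1 states, "Deaths and SAEs occurring after the 30-day safety follow-up period AND considered related to study treatment or study procedures must also be reported". Section 10.1.2 counts a congenital anomaly or birth defect as a serious outcome.

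**The concern.** The reporting period ends while the avoidance period is still running, and neither document explains why. If conception is unsafe enough to be avoided until month 3, a conception before month 3 is an exposure the sponsor needs to know about. Under the current text, an ongoing or uncomplicated pregnancy conceived after day 60 creates no duty for the subject or the investigator. The sponsor could be left with no pregnancy record and no 1-year infant outcome. This is a matter of patient and fetal safety. It does not touch the comparison of the treatment groups.

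**Working it through.** The plan gives no calculated figure to reproduce. The check is calendar arithmetic, a search for any other provision that closes the gap, and a rough event count.

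**Length of the gap**

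- Reporting ends at day 60 after the last dose (Section 10.2.3).
- The minimum avoidance period is 3 months (criterion 7). It is counted here from the last dose, taking completion of treatment as the last dose.
- At 30 days per month, the convention SAP Section 7.3.5 uses for analyses, 3 × 30 − 60 = 30 days.
- Three calendar months last 89 to 92 days depending on the start date, so the gap is 89 − 60 = 29 to 92 − 60 = 32 days.

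The gap concerns conceptions after day 60. A pregnancy that occurs by day 60 and is discovered later is still covered.

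**Whether another provision closes it**

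| Provision | After day 60 | Effect on the gap |
|---|---|---|
| Abortion reporting (10.2.3) | No time limit | Catches pregnancies that end in abortion, including spontaneous |
| Late serious adverse events (10.3.1) | Only if considered related | Can catch a related birth defect, but requires no pregnancy record or routine infant follow-up |
| Pregnancy testing (9.5.5) | Last listed test is at the safety visit, 30 (+7) days after the last dose | None; 90 − 37 = 53 to 90 − 30 = 60 days of the avoidance period follow that test |
| Long-term follow-up (9.5.6) | Contacts continue until death | None; no pregnancy test or enquiry is listed |

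The Table 16 grid cannot be read in the supplied text, so the last two rows rest on the visit descriptions.

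**Likely number of events**

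The documents do not say how many subjects are, or have partners, of child-bearing potential. Assume that 0 to 5% of 800 subjects (0 to 40) are, and that 1 to 10% of these conceive per year:

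- Upper bound: 40 × 0.10 × 30/365 = 0.33 pregnancies.
- Lower bound: 0.
- Upper bound for the roughly 400 subjects assigned SGI-110 alone: 20 × 0.10 × 30/365 = 0.16.

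These figures make no allowance for deaths, which would lower them.

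**The case against.** The two periods serve different purposes. Criterion 7 governs conduct and Section 10.2.3 governs reporting; both can be obeyed at once, and no rule in the documents says they must be equal. That is correct: this is a design choice rather than a contradiction. It still leaves part of the avoidance period without pregnancy reporting, and no reason is given.

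The expected count is well below one. Eligibility is age 75 or over, or younger and unfit, and the median age in the Phase 2 treatment-naïve cohort was 77. This stands, and it keeps the point minor.

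The sentence on completing Part I refers to any occurrence of pregnancy and could, read alone, be taken as unlimited. It directly follows the time-limited sentence and says how to carry out that report, and the next paragraph repeats the 60-day limit. The limited reading is the natural one. A site could report a later pregnancy voluntarily; the protocol does not require it.

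The consent form is not available and may ask for more. It would not change the investigator's reporting limit as the protocol states it. Amendment 1 (Appendix 5, item 1) brought in the 3-month contraception requirement and does not list Section 10.2.3 among the sections changed. That suggests an oversight but does not prove one, and the point does not depend on it.

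Finally, moving the limit adds no question to the follow-up contacts, so capture would still depend on subjects volunteering the information. This is a fair limitation. The change would, however, give subjects a duty to inform that they do not have now.

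**Conclusion.** The concern holds, at low severity. For about 30 days (29 to 32) the protocol requires conception to be avoided but does not require an ongoing pregnancy to be reported or its infant followed. This is a minimum, because criterion 7 says at least 3 months. It is a length of time, not a share of the risk. What goes uncaptured is ongoing or uncomplicated pregnancies; abortions and serious events judged related remain reportable. The mismatch and its length rest on the protocol text and confidence in them is high. The event count of 0 to about 0.3 rests entirely on assumed fertility and conception rates.

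**What to change.** In both sentences of Section 10.2.3 that carry the limit, replace 60 days after the last dose with at least 3 months after the last dose, and align any matching consent wording. Do not shorten the contraception period in criterion 7 to make the two agree.

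The gap then falls from about 30 days to 0. The cost is two identical edits and a slightly longer safety-reporting period. No new visits are needed: long-term contacts already continue until death, and Section 9.5.6 states, "Long-term follow-up visits may be conducted by telephone if needed". If the sponsor wants more than spontaneous reports, a single pregnancy question at the first such contact after the 3-month point would be enough.
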